### Gait training

Each group will undergo twelve 2 hour sessions of standard gait training (up to 3x/week based on availability). Both groups will receive the same gait training while the treatment group will receive gait training with CV and control group without it.

Up to four vibrators per leg powered by the vibration stimulation control unit (VSCU) will be strapped or taped over ankle dorsiflexor tibialis anterior (TA), knee extensor and hip flexor rectus femoris (RF), knee flexor short head of biceps femoris (BF) and hip flexor and abductor the lateral portion of tensor fasciae latae muscles (TFL) as shown in figure. The cylindrical vibrators will be used to increase vibration intensity as needed. The CV paradigm resembling normal activity of muscles timed to gait events, as detected by accelerometers taped to the shoes and force sensing resistors placed in the insoles, will be imposed during walking. An average frequency of vibration will be set at 80Hz and as high as 150Hz. Physical therapist will conduct all gait training and encourage maximal voluntary effort during training while providing standby assist and spotting the subjects to ensure safety. During walking, heart rate (HR) will be monitored with the chest strap monitor and receiver watch and recorded before and after each walk. Blood pressure (BP) will be measured before and after each session of CV training and evaluation. In addition, subjects will be asked during each session if they experience any untoward sensation. BP and HR during gait training with vibration will be monitored and compared to baseline values. An increase in BP and HR of >20% and experiencing untoward sensation will be considered significant to reject Hypothesis that CV produces no physiological changes.

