#### 10. Describe the means of analyzing the data and evaluating the results.

- *State the anticipated methods to be used for analysis and interpretation of the data.*
- *The methods must compliment the design of the study and the nature of the data which is being collected.*

Primary outcome measures for testing hypotheses will be walking speed measured during 10m walk trials and foot-to-floor clearance as measured by vertical displacement of marker placed over the first metatarsal using our 16-camera VICON motion analysis system. Force sensing resistors (FSRs) will be used to detect any toe dragging as a result of insufficient foot clearance. Secondary measures will be peak hip, knee and ankle flexion during swing, hip-knee coordination changes, knee flexion during stance and in pre-swing, step length symmetry and 6min walking distance.

The within subject experimental design will be used because it requires fewer subjects with more statistical power while reducing the potential for systemic error or selection bias to test the effect of CV on walking. While practice and carryover effects are major disadvantages of this study design, proper precautions including rest periods between tests and randomization of testing order for treatment group will be instituted to minimize them†. In addition to comparison between treatment and control groups, subjects receiving CV can also serve as their own controls by first comparing volitional gait at baseline (VGB) with any gait correction with the CV approximating desired normal muscle activity (CVN). Next the volitional gait *post*- 12 sessions of training with vibration (VGP) will be compared to volitional gait at baseline (VGB). Thus, any improvements at baseline with CVN compared to volitional gait (VGB) can be attributed to short term effects of vibration. Improvements in volitional gait *post* training with vibration (VGP) compared to baseline gait (VGB) will be attributed to long term effects of vibration. The control group subjects will be evaluated at baseline (VGB) and after gait training (VGP) and compared to the intervention group to identify trends and further explore the potential effects of CV. While this study design has limited generalizability due to the inhomogeneity of the selected population, it can be quite useful for developing and refining CV intervention.

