**Recruitment and baseline evaluation**

Potential subjects will be identified via chart review or through referral and asked if they would be willing to participate in the study. If agreeing, they would undergo the consent process. Twelve subjects with gait disorders from MS will be recruited for participation in this study, with six subjects assigned to undergo CV gait training and six to control group for gait training without vibration. Subjects will be randomly assigned to either treatment or control group and matched by functional walking category based on speed for data analysis†. After signing the consent form agreeing to participate in the study and meeting inclusion/exclusion criteria, subjects will undergo baseline evaluation. This will include walking speed and distance and using VICON system for temporal and spatial parameters, kinematics and kinetics of gait and EMG activity during volitional gait at their preferred walking speed.

Retro-reflective markers will be placed on the bony landmarks and surface EMG electrodes over target muscles while the subject walks along the 10m walkway instrumented with force platforms. Standard analysis software provided with VICON system will be used to track markers in 3D and calculate all gait parameters so they can be correlated with muscle activity. The baseline evaluation will be done with and without vibration on treatment group and without vibration on control group. Data will be collected during 6 walking trials of at least 5 steps per trial (approximately 30 steps) within the visual field of the VICON motion analysis system under each condition. Sufficient resting time will be provided between trials to complete the assessment. Subjects will be encouraged to use their walking aid while a trained physical therapist provides standby guard during walking for their safety.

[figure not shown]

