**14. Will the research involve the following?**

N/A **Chart/Data Review**

**Placebo Group**  No  Yes (*describe*):

**Other Control Group**  No  Yes (*describe*): Will be individuals with gait deficits from MS who will undergo the same gait training as treatment group but without cyclical vibration as described under #13 "research design and all study related procedures".

**Randomization**  No  Yes (*describe*): Subjects will be randomly assigned to either treatment or control group using a coin toss.

**Deception**  No  Yes (*describe*):

**15. Does the research involve the use and/or disclosure of Individually Identifiable Health Information in any form or medium?**

No  Yes **If yes, complete the required HIPAA Waiver/Authorization forms.**

**16. Does the study include the administration of a study agent that does not require FDA approval and does not require an IND (e.g. vitamins, food supplements, isotope tracers, alternative medicines, etc.)?**

No  Yes *-provide a detailed description of the procedures used to assure patient safety:*

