a. Who will have access to the key? PI, physical therapist, study coordinator/staff

b. Where is the key maintained? Two locking barriers must be in place between the coded data and the key. Motion Study Laboratory, B-B322, locked file cabinet, in a locked room.

- De-identified-by Privacy Officer or Statistician.

- Other (*describe*):

57. How will electronic research data be secured while the study is active?

- No electronic data will be stored
- VA encrypted laptop
- Encrypted VA device/media- describe:

- VA network drive;
  - M: drive; whose?
  - S: drive
    - Folder access password protected
  - Other drive location (for example P: drive):
    - Folder access password protected

58. How will hardcopy research data be secured while the study is active? Two locking barriers must be in place.

- No hardcopy data will be stored
- Locked office and locked file cabinet
- Data coded by PI or study staff with a master list secured and kept separately
- Data de-identified by Privacy Officer or Statistician- (VA does not consider coded data to be de-identified)
- Other -specify:

59. Provide the physical location including room number (and address if outside of this VA) where all electronic and hardcopy data will be stored: B-B322

60. Is identifiable information physically or electronically sent TO the LSCDVAMC from other institutions or locations?

- No  Yes - contact Privacy Officer [name] or [name] [[contact]](mailto:[contact]) / [contact] [[contact]](mailto:[contact]) / [name] or Information Security Officer [name] [[contact]](mailto:[contact]) / [contact] – prior to submitting to the Research Service.

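### Gains are attributed to vibration itself, but the plan does not state what hardware is worn in each condition and describes no masking of gait-data processing

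*Protocol*

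**What the plan says.** **Arms.** Protocol Section 3, item 13 (Gait training): "Both groups will receive the same gait training while the treatment group will receive gait training with CV and control group without it". Item 14 describes controls as people with MS "who will undergo the same gait training as treatment group but without cyclical vibration as described under #13".

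**Hardware.** Item 13 (Gait training): "Up to four vibrators per leg powered by the vibration stimulation control unit (VSCU) will be strapped or taped over ankle dorsiflexor tibialis anterior", with further sites over the thigh and hip muscles. The sentence does not name the arm or test condition in which they are mounted.

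**Test conditions.** Item 13 (Recruitment and baseline evaluation): "The baseline evaluation will be done with and without vibration on treatment group and without vibration on control group". Post-training testing is also described only as with and without vibration.

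**Attribution.** Item 10 says that "any improvements at baseline with CVN compared to volitional gait (VGB) can be attributed to short term effects of vibration", and that improvement in volitional gait after training "compared to baseline gait (VGB) will be attributed to long term effects of vibration". The SAP repeats both statements. The between-arm comparison is described in item 10 as a search for trends.

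**Safeguards.** Item 10 and the SAP name rest periods and randomised testing order, aimed at practice and carryover. Neither document mentions masking of subjects, therapist or data processors. The subject code appears under confidentiality (Section 5, item 38; Section 7, item 56), and its key is held by "PI, physical therapist, study coordinator/staff" (item 56a).

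**The concern.** To attribute a difference to vibration, the two conditions should differ in vibration and as little else as possible. Here the documents leave three other differences open.

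- **Hardware.** If the vibrators and control unit are off the body in the reference condition, the contrast also contains their load and the strap or tape contact over the target muscles.
- **Expectation and effort.** Subjects know when vibration is on. Walking speed, one of the two primary outcomes, depends on effort.
- **Processing.** If marker tracking, stride selection and clearance extraction are done knowing arm and visit, discretionary choices can lean towards the hypothesis.

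The VGP-VGB contrast in the treated arm has a further difference: 12 sessions of gait training fall between the two assessments.

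The pilot is meant to show whether vibration warrants a full study (item 9) and to supply the data that will size it (item 11). A non-specific effect read as a vibration effect would pass into both.

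**Working it through.** **1. The plan's own figure.** Item 11 and the SAP give 6 trials x about 5 strides = 30 strides per condition, and the product agrees. The 90% power behind it cannot be reproduced, because no effect size, SD or sidedness is given. Inverting the normal formula at two-sided 0.05, 30 per condition implies (1.960 + 1.282) x sqrt(2/30) = 0.84 SD for two independent samples, or (1.960 + 1.282)/sqrt(30) = 0.59 SD for paired data. Nothing below depends on these values. More strides improve precision but do not remove a systematic difference between conditions.

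**2. What each contrast contains.**

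| Contrast | Plan's reading | Also changes, or may change |
|---|---|---|
| CVN-VGB, treated arm | Short-term effect of vibration | Expectation and effort; hardware, if not mounted in VGB (not stated) |
| VGP-VGB, treated arm | Long-term effect of vibration | 12 training sessions; expectation and effort; hardware, if its state differs between visits (not stated) |
| Change VGP-VGB, treated v control | Trends only | Expectation and effort; hardware worn in training, if controls have none (not stated). Training itself is common to both arms |

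Only the third row removes the effect of training, yet the firm attribution statements belong to the first two.

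**3. Exposure.** The treated arm trains with up to 4 x 2 = 8 vibrators for 12 x 2 h = 24 h. The documents give no corresponding figure for hardware on controls.

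**4. How much a non-specific effect could matter (illustration).** The documents give no value for such an effect, nor any device mass or measurement reliability. Assume normal data, no true vibration effect, and a non-specific shift of b SD in favour of vibration. A t-test at two-sided 0.05 stands in for the planned ANOVAs. The chance of a significant result in favour of vibration is P(T > t_crit), where T is noncentral t:

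- Between arms, 6 v 6: df = 10, t_crit = 2.228, noncentrality = b x sqrt(6/2) = 1.732b.
- Paired, six treated subjects (b in SDs of the difference): df = 5, t_crit = 2.571, noncentrality = b x sqrt(6) = 2.449b.
- One subject, 30 v 30 strides treated as independent (b in stride SDs): df = 58, t_crit = 2.002, noncentrality = b x sqrt(30/2) = 3.873b.

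| b | 6 v 6 | Paired, n = 6 | 30 v 30 strides |
|---|---|---|---|
| 0 | 2.5% | 2.5% | 2.5% |
| 0.2 | 5% | 6% | 12% |
| 0.5 | 12% | 17% | 48% |
| 0.8 | 24% | 36% | 86% |

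The last column applies only if strides within a subject are the unit of analysis. The SAP's per-subject means and SDs allow that reading but do not settle it.

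**5. Reach of the between-arm comparison.** With 6 per arm, 80% power needs (1.960 + 0.842) x sqrt(2/6) = 1.6 SD by the normal formula, or about 1.8 SD with the t distribution. It is the right basis for a long-term claim, but at this size it is exploratory.

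**The case against.** The strongest reply is that silence is not evidence. A reader might infer that controls train with no hardware, that volitional trials are walked without it, and that all data are processed unmasked. The documents state none of these. Without vibration can mean mounted and switched off, and randomised testing order within a session makes that plausible for the treated arm. Holding a confidentiality key does not show who tracks markers or selects strides. This objection stands, so the point is that hardware and masking are unspecified and that the attribution goes further than the described design supports.

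Other parts of the reply also stand:

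- Outcomes come from marker-based kinematics and standard software, which limits assessor discretion without removing it.
- Force sensors also serve as outcome sensors for toe drag, and EMG electrodes are placed at baseline without distinction by arm. Any hardware argument therefore rests on the vibrators and control unit.
- It might be inferred that one therapist treats both arms and urges effort in scored trials. Item 13 mentions encouragement of effort only during training, and sets baseline gait analysis at preferred speed. No change to scored-trial instructions is needed on this ground.
- Fitting controls with unpowered vibrators for 24 h of training adds strap and tape burden. It cannot remove expectation: entry requires tolerating muscle vibration (item 30) and the device is demonstrated at consent (item 48).
- Hypothesis 2 concerns gait maintained after application, so hardware in every volitional trial could alter the outcome it is meant to measure.

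The exploratory label on the between-arm comparison does not answer the point, because the within-subject statements are worded as attribution. Randomised order and rest periods address practice and carryover; they do not address expectation or hardware.

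**Conclusion.** The point holds as a gap in specification together with an over-wide conclusion. The documents leave open what is worn by controls and in volitional trials and describe no masked processing, yet they assign CVN-VGB and VGP-VGB gains to vibration itself. The clearest case is VGP-VGB in the treated arm, where the plan's own 12 training sessions are an alternative explanation whatever the answer on hardware. For CVN-VGB, expectation and effort remain in any event; a hardware difference is possible but not shown.

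The size of any bias is unknown. The 6% to 36% range for paired tests rests wholly on an assumed non-specific effect of 0.2 to 0.8 SD and on a t-test in place of the planned ANOVA. The documents do not support saying that the comparator lacks the hardware, that control exposure is zero, or that data handling is known to be unmasked. This is a worthwhile, inexpensive improvement; it does not invalidate a feasibility study.

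**What to change.** 1. **Mask processing (item 13).** Save volitional VICON trials under random file codes that hide arm and visit until marker tracking, stride selection and clearance extraction are finished. Cost: file renaming and a held code list. The SAP is written in the past tense; if collection is complete, retained files can still be reprocessed this way.
2. **Narrow the conclusion (item 10 and SAP).** Refer to open-label walking or training with the vibration system, not to vibration itself. Base any long-term claim on the between-arm comparison of VGP-VGB change, not on the treated arm alone. Cost: wording, and a more modest claim.
3. **State the hardware (item 13).** Say what is worn in each arm, visit and condition. For the baseline short-term contrast in the treated arm, walk the without-vibration trials with the vibrators mounted and unpowered, so that CVN and its reference differ in vibration and not in hardware. Keep VGB and VGP in the same hardware state for the long-term contrast. If that state is hardware off, the treated arm needs a separate baseline reference set of about 6 more trials (30 strides). Cost: a little set-up, plus those trials if chosen. If collection is complete, report what was worn.

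Unpowered vibrators for controls during training are optional. They would equalise hardware but not expectation, at the burden noted above.

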The primary goal of this pilot study is to explore the feasibility of cyclic vibration of the lower extremity muscles to improve walking in veterans with gait deficits from MS. Vibration is perhaps the most potent mechanical stimulus for activating muscle spindle primary afferents (Ia) [1]. This facilitates excitability of corticospinal projections to the target muscles while the  $\alpha$ -efferents to antagonists are inhibited. Since it has been shown that cyclical vibration promotes normal patterns of motor activity by modulating the excitability of motoneurons projecting to target muscles, *it is hypothesized that facilitatory effects of cyclical muscle vibration of hip, knee and ankle muscles improves 1) walking speed and foot-to-floor clearance through increased hip and knee pre-swing flexion and improved hip-knee coordination, 2) induces carryover effects that maintain improved walking after application and 3) produces no untoward sensations or adverse physiological responses.* In previous studies vibration to the dorsiflexor muscle tibialis anterior [2] alone and in combination with the hip abductor gluteus medius [3] resulted in improved walking speed in individuals with hemiplegia. Similarly, cyclical vibration increased muscle excitation with phase dependent changes in the timing of muscle activation during gait [4] and multi-channel complex vibration patterns exhibited gait-like leg movements that present a potential for rehabilitation [5].

Therefore, this pilot study is designed to explore the efficacy and safety of cyclical vibration at correcting the typical gait deficits that involve strength and coordination of multiple joints (hip, knee and ankle) in pre- and early swing and determine whether the new intervention warrants a full comprehensive study to quantify its facilitatory effects on gait improvement in veterans with MS.

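### The only rejection rule for the safety hypothesis does not match that hypothesis: read literally it needs all signs at once, and its BP/HR part has no defined baseline or stated exertion-matched comparison

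*Protocol*

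**What the plan says.** Protocol item 9 lists three hypotheses. The third is that cyclical vibration (CV) "produces no untoward sensations or adverse physiological responses".

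Protocol item 13, Gait training, gives the only criterion for judging it: "An increase in BP and HR of >20% and experiencing untoward sensation will be considered significant to reject Hypothesis". The sentence continues so that the criterion serves to "reject Hypothesis that CV produces no physiological changes".

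The same paragraph describes the data. HR is "recorded before and after each walk". For BP: "Blood pressure (BP) will be measured before and after each session of CV training and evaluation". For sensations: "subjects will be asked during each session if they experience any untoward sensation". The comparison is given as: "BP and HR during gait training with vibration will be monitored and compared to baseline values".

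Protocol item 10 applies its ANOVA to Hypotheses 1 and 2 and its pairwise tests to gait measures. The SAP describes an ANOVA on outcome means and mentions neither BP, HR, sensations nor a safety hypothesis.

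**The concern.** The hypothesis joins its two kinds of event with 'or', so one untoward sensation is enough to contradict it. The rejection rule joins its signs with 'and', twice. Followed to the letter, repeated untoward sensations without a BP and HR rise would leave the hypothesis standing, and the trial could report that its safety hypothesis was not rejected while its own records contradict it.

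The BP/HR part can err in the opposite direction. Training is done at full effort, the reference readings are not named, and no comparison with equally effortful walking without vibration is stated. If any single sign is enough, a rise caused by exercise could be counted against vibration.

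Item 9 says that the pilot explores safety and is to "determine whether the new intervention warrants a full comprehensive study", so the safety statement will be read by whoever plans the next study.

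**Working it through.** The documents give no sample size, error rate or expected event rate for Hypothesis 3, so there is no stated figure to reproduce. The check compares the texts and counts outcomes under each reading.

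**Step 1. Readings of the rule.** Take three yes/no signs: BP up by more than 20%, HR up by more than 20%, untoward sensation. The sentence can be read as (A) all three together, (B) BP and HR together, or a sensation, or (C) any one sign. There are 2 × 2 × 2 = 8 patterns.

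| BP | HR | Sensation | A | B | C |
|---|---|---|---|---|---|
| no | no | no | keep | keep | keep |
| yes | no | no | keep | keep | reject |
| no | yes | no | keep | keep | reject |
| yes | yes | no | keep | reject | reject |
| no | no | yes | keep | reject | reject |
| yes | no | yes | keep | reject | reject |
| no | yes | yes | keep | reject | reject |
| yes | yes | yes | reject | reject | reject |

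A rejects in 1 pattern, B in 5 and C in 7. All three agree in 2 (first and last rows) and differ in 8 − 2 = 6. Four patterns include a sensation and so contradict Hypothesis 3 as worded; A keeps the hypothesis in 3 of those 4. These counts show how far the readings diverge logically. They are not probabilities, and if the signs always occurred together the readings would coincide.

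**Step 2. Does another passage choose between the readings?** The 'or' in item 9 points to B or C for sensations. Item 10 and the SAP say nothing on it. Whether BP and HR are judged jointly (B) or separately (C) is nowhere stated.

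**Step 3. Unit.** The rule does not say what it applies to. With 6 treated subjects and 12 sessions each, it could be 6 × 12 = 72 training sessions, 6 subjects, or one group mean. It could also apply to each walk.

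**Step 4. Reference readings.** The candidates are the pre-walk HR and pre-session BP in item 13, or readings from the baseline evaluation. The second is weaker: the baseline evaluation text in item 13 lists no BP or HR, and only the words on BP timing under Gait training reach evaluations. That evaluation is also walked at a self-chosen speed, whereas training asks for the fullest effort. To show the size of the HR criterion, for assumed reference rates of 70 and 80 bpm it is passed above 70 × 1.2 = 84 and 80 × 1.2 = 96 bpm. The choice of reference therefore matters.

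**Step 5. No-vibration data.** Two sources may exist. The control arm does the same training without CV: HR monitoring during walking is not limited to one arm, but BP is scheduled around CV training and evaluation, so BP at control training sessions is uncertain. The treated subjects are also evaluated with and without vibration, at baseline and after training (item 13), and the SAP reports randomised testing order for these conditions. If the per-walk HR recording covers those walks, a within-subject HR comparison is available. Neither comparison is stated for BP, HR or sensations; the between-group comparison in item 10 is described for gait.

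**Step 6. Precision, relevant to the fix only.** For 6 against 6, the 95% half-width for a difference in means is t(0.975, 10) × √(1/6 + 1/6) = 2.228 × 0.577 = 1.29 SD. In one arm, 0 of 6 has an exact 95% upper limit of 1 − 0.025^(1/6) = 46%. These limits would be the same under a perfectly worded rule.

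**The case against.** The strongest reply is that the meaning is clear enough. Only the third hypothesis concerns physiological responses, item 9 uses 'or', and the authors very probably meant a list of warning signs. Much of this stands: the literal reading is the less plausible one. But the rule as printed supports it, no other text excludes it, and the list reading leaves open whether BP and HR count jointly or separately.

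A reader might infer that the rule tests a different hypothesis altogether, because it speaks of no physiological changes. The documents do not support that. It is a loose paraphrase of Hypothesis 3, and untoward sensation stays in the rule.

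A reader might also infer that a BP or HR rise can never be separated from exertion in this trial. That goes too far, given the control arm and the with- and without-vibration evaluations in the same subjects. What holds is that no exertion-matched comparison is stated. The within-subject evaluations have limits too: they are not full-effort training, and BP is taken per session rather than per condition.

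Finally, this is a 12-subject feasibility study, labelled minimal risk in item 66, in which BP, HR and sensations are neither primary nor secondary outcomes. That limits the weight of the point but does not remove it, since safety is one of three stated hypotheses.

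**Conclusion.** The concern holds as a mismatch between a hypothesis and its only decision rule. The same records can lead to opposite conclusions on Hypothesis 3: the readings differ in 6 of 8 sign patterns, and the literal one keeps the hypothesis in 3 of the 4 patterns that include a sensation. No event rates are assumed, so this says nothing about how often it would happen. Entry required that vibration be tolerated without untoward sensation (item 30), which makes that sign less likely.

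The two weaknesses pull in opposite directions: the literal wording favours a clean safety result, while the uncontrolled BP/HR comparison under the list reading could overstate harm.

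Two stronger inferences are not supported. Harm would not go unnoticed: sensations are asked about in each session, adverse events are reported (item 53), and removal from the study (item 65) does not depend on this rule. Nor do the documents tie the decision on a full study to this rule alone. What is at stake is the safety conclusion of a small pilot; the gait analyses are unaffected. The point should be corrected, but it is not a fatal flaw.

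**What to change.** Reconcile items 9 and 13 so that the rule refers to Hypothesis 3, and carry it into the SAP in a short safety paragraph.

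- **Components.** Assess untoward sensation and the BP/HR response separately, per subject, and state that an untoward sensation alone counts against Hypothesis 3. The sponsor must state whether BP and HR are judged jointly or separately under its own >20% criterion, and how many exceedances over the 12 sessions count.
- **Reference.** Name the readings used as baseline, for example the pre-walk HR and pre-session BP already planned.
- **Comparison.** Interpret a BP/HR rise as a vibration effect only beside no-vibration data already recorded: the control arm's HR and any BP, and, where recorded, HR with versus without vibration in the same subjects at the evaluations. Report this descriptively with 95% confidence intervals, because 6 per arm allows no more.
- **Timing.** The SAP is written in the past tense. If data are already collected, label the revised rule post hoc and show the result under the literal wording beside it.

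The cost is one reworded rule, one SAP paragraph and, at most, a re-analysis of readings already on file. No new subjects or measurements are needed. The downside is a less favourable and less precise safety statement.

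### A >20% cut on heart rate and blood pressure cannot support a conclusion of no physiological change, and no other analysis of these readings is planned

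*Protocol*

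**What the plan says.** Hypothesis 3, in protocol item 9, is that cyclical vibration (CV) "produces no untoward sensations or adverse physiological responses". Item 13 (Gait training) sets out the data: "heart rate (HR) will be monitored with the chest strap monitor and receiver watch and recorded before and after each walk", and "Blood pressure (BP) will be measured before and after each session of CV training and evaluation". On use of the data it says "BP and HR during gait training with vibration will be monitored and compared to baseline values", and then gives the rule: "An increase in BP and HR of >20% and experiencing untoward sensation will be considered significant to reject Hypothesis that CV produces no physiological changes".

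The allocation is "six subjects assigned to undergo CV gait training and six to control group for gait training without vibration", and "Each group will undergo twelve 2 hour sessions of standard gait training". At baseline, "The baseline evaluation will be done with and without vibration on treatment group and without vibration on control group".

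Item 10 assigns the repeated-measures ANOVA to Hypotheses 1 and 2, and its primary and secondary measures do not include HR or BP. The SAP describes means, standard deviations and a two-way ANOVA for the outcome measures. It mentions neither HR, BP nor Hypothesis 3.

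**The concern.** The statement under test in item 13 is that vibration causes no physiological change. A threshold of 20% does not examine that statement: a rise of 10 or 15% in every subject scores the same as no rise. The readings that could tell these cases apart are collected, but no estimate or interval is planned for them.

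Safety is one of the pilot's stated aims (item 9), and the pilot is meant to supply preliminary data for a larger study (item 11). If the rule is not met, the natural report is that no physiological change was found. That would carry no figure for how large a change the data exclude, which is what the planners of the next study need.

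**Working it through.** **Plan's own figure.** There is none to reproduce. The documents give no derivation of the 20% value, no SD for HR or BP change, and no power for this rule. The 90% power in item 11 and the SAP concerns the number of strides.

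**1. Is there another analysis of HR or BP?** Item 10 limits the ANOVA to Hypotheses 1 and 2 and does not list HR or BP as measures. Item 13 plans a comparison with baseline values but names no estimate, test or interval, and the next sentence in that section on their use is the cut. The SAP's ANOVA covers outcome measures without naming these two. No other analysis is specified.

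**2. A consistent rise below the cut (no assumed SD needed).** Take six vibrated subjects (item 13).
- If all six rise, by any amount, the exact two-sided sign test gives p = 2 × 0.5⁶ = 0.031.
- Illustration: rises of 8, 9, 10, 10, 11 and 12%. Mean = 60/6 = 10%. SD = √(10/5) = 1.41. SE = 1.41/√6 = 0.577.
- 95% CI = 10 ± 2.571 × 0.577 = 8.5 to 11.5%. Paired t = 10/0.577 = 17.3, p = 0.00001.
- Subjects above 20%: none of six. The rule does not reject.

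**3. What six subjects could show (assumed SDs).** Assumptions, in percentage points: between-subject SD 5, SD of a single reading s = 8 (range 5 to 10), SD of the vibration effect between subjects 4, two-sided alpha 0.05.
- Paired contrast, six walks with and six without vibration: SD of a subject's difference = √(4² + 2s²/6). At s = 8 this is √(16 + 21.3) = 6.11. For a true effect of +10, power from the noncentral t on 5 df is about 89% (97% at s = 5, 79% at s = 10).
- Same contrast, true effect +5: about 37% (52% to 30%).
- Six v six on 12-session subject means: SD = √(25 + 16 + 64/12) = 6.81 in the vibrated arm and √(25 + 64/12) = 5.51 in control. For +10, simulated power is about 71% (75% at s = 5, 68% at s = 10).

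**4. Does a before-to-after change in vibrated subjects alone isolate vibration?** Suppose vibration does nothing but the training session raises the reading. With SD 5.51 and n = 6, the 95% CI for the mean change excludes zero in about 44% of trials for a 5-point exercise rise and 94% for a 10-point rise. An uncontrolled mean therefore cannot be read as a vibration effect.

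**The case against.** The strongest reply is that item 9 speaks of adverse responses. Under that wording a pre-stated size of rise is a reasonable marker of adversity, and a 10% rise during effortful walking need not be adverse. This stands as far as it goes: the cut may serve as an individual safety flag. It does not rescue item 13, which uses the cut to decide on a statement of no change. The two wordings differ and need to be reconciled.

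Second, a rise during training mixes vibration with exercise. This also stands (step 4) and limits the remedy. The BP sentence refers to CV sessions, so control-group BP may not exist. HR recording is described under gait training, so it is not certain that it covers the evaluation walks.

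Third, HR and BP are not listed outcomes in this small feasibility study. That is true and limits how much rests on the point, but Hypothesis 3 is still one of three that the protocol sets out to test.

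A reader might go further and infer a specific low power or a high false-alarm rate for the rule. The documents do not support either. They plan no between-arm test of threshold counts, and they do not say whether the cut applies to a reading, a subject or the group mean. Read literally, the rule also needs BP, HR and an untoward sensation together. Nor do the documents show that 20% is a wrong safety value.

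**Conclusion.** The point holds: the only stated rule for the physiological part of Hypothesis 3 reduces numeric data to a cut, and that cut cannot support a conclusion of no change. The uniform-rise example (none of six above 20%, sign test p = 0.031, CI 8.5 to 11.5%) needs no assumed SD. It shows what can happen, not what is likely.

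The power figures rest wholly on assumed SDs. They suggest that a 10-point effect would usually be detectable on the continuous scale (about 89% paired, about 71% between arms), while a 5-point effect would often be missed (about 37% paired). In the second case an interval would show the uncertainty, which a yes/no verdict hides. The change should be made, but it does not touch the primary gait outcomes.

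**What to change.** In protocol item 13 and in the SAP:

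1. Keep the >20% value unchanged as an individual safety flag, report it as a count, and state which readings and which baseline it refers to.
2. Replace the sentence that rejects the hypothesis with the mean within-subject percent change in HR and in BP, each with a 95% CI and with subjects as the unit of analysis.
3. Attribute a change to vibration only through a contrast. For HR, use CV versus control training sessions, or evaluation walks with versus without vibration once it is confirmed that HR is recorded there.
4. Describe the before-to-after session BP change in vibrated subjects as a change under training with CV, unless control-group BP is also recorded.
5. Reconcile the wordings of Hypothesis 3 in items 9 and 13.

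The cost is wording and one summary of readings that are mostly already planned. No extra subjects or visits are needed, but the sponsor must confirm which HR and BP readings exist for control sessions and evaluation walks. The downside is that the conclusion becomes an estimate, probably with a wide interval, in place of a yes/no verdict.
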